# Methods and documentation

# Study design and methodology

This is a multi-centre, observational, non-interventional study, which will prospectively collect clinical and socio-demographic data from patients with depression occurred after COVID 19 in real clinical settings during 8 weeks of treatment.

At Visit 0 (V0), investigating psychiatrist or neurologist will evaluate patient's eligibility for the study according to inclusion/non-inclusion criteria. Only patients who comply with all inclusion/ non inclusion creteria will be invited to participate in this observational study. Recommendation to start treatment with agomelatine to manage depressive episode is to be done by investigating psychiatrist/ neurologist before and independently from the decision to invite a patient to participate in the study. Agomelatine should be administered to patients in accordance to the instruction for medical use approved in the Russian Federation (RF).

20 clinics and 20 of psychiatrists and neurologists across the country will participate in the study and it is estimated that each investigating physician will enroll at least 5 of patients.

Once a patient will provide his/her consent to participate in the study, investigating physician will record information from appointments for the evaluation of treatment in a routine clinical practice. The frequency of the appointments reflects a routine clinical practice of management of outpatients with depressive disorders in the RF.

Main millestones:

Local Ethic Committee approval – 1q22 First patient included – March 2022 Last patient included – July 2022 End of treatment period – September 2022 Clinical statistic subdevelopment – August 2022 Data based lock – October 2022 Clinical statistic subdevelopment report – November-December 2022 End of clinical study – February 2023

# Selection of the study population

# **Inclusion criteria**

- 1. Obtained signed informed consent from the patient.
- 2. Age of 18-65 years old.

- 3. Out-patient with confirmed COVID 19 infection within 3 months period before the date of inclusion.
- 4. Confirmed depression with total HAMD-17 score of 8-24 required treatment with antidepressive medicines.
- 5. Decision to administer agomelatine preceeds the decision to include a patient in the study.

# Non-inclusion criteria

- 1. Current participation in any clinical trial or during 30 day period from inclusion visit.
- 2. Suicide risk (accoding clinical evaluation of investigator).
- 3. Psychotics symptoms (according clinical evaluation of investigator).
- 4. Schizophrenia, schizo-affective disorders, organic damages of CNS, dementia, epilepsy, multiple sclerosis, Parkinson disease, Alzeimert disease, Bipolar disorders.
- 5. Alcohol abuse or drug addiction in anamnesis.
- 6. Severe or decompensated somatic or neurological disorders.
- 7. MAO inhibitors during last 2 weeks.
- 8. Treatment by others psychotropic products (antipsychotics, anxiolitics etc.).
- 9. Any contraindications to agomelatine in accordance to the local SmPC.

# **Exclusion criteria**

- 1. Patients with severe/decompensated psychiatric, somatic or neurological disorders.
- 2. Patients with any sign of liver failure (increase of transaminase up to 3 times higher), which needs to stop treatment with agomelatine.
- 3. Patients who participate in any clinical trial or survey.

**Therapeutic strategy during the study** The assignment of a subject to a particular therapeutic strategy is not supposed by this protocol due to the observational nature of the study. Treatment approaches to depressed patients are based on local clinical recommendations and clinical experience of HCPs. Decision on agomelatine administration must be made with accordance to established SmPC, local standards and guidelines and must be independent from and proceeding the decision of the physician to include a patient in this study.

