## Study variables

## **Primary variables:**

• Mean change from baseline (BL) in total HAMD-17 score assessed at week 8 of the observational period.

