## Table 1 – Planned study visits and collecting parameters at each visit

Procedure	Inclusion Visit 0	Visit 1 at W2	Visit 2 at W4	Visit 3 at W8
Written informed consent	X			
Assessment in accordance to inclusion/ non- inclusion criteria	X			
Assessment in accordance to exclusion criteria		X	X	X
Demographics	X			
HAMD-17	X	X	X	X
CGI -I		X	X	X
SF-36	X	X	X	X
Current treatment with other concomitant medications	X	X	X	X
Adverse events/drug reactions/ special situations reporting		X	X	X

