#### Data collection at the Final Visit (V3 - week 8):

- HAMD-17 score.
- CGI-Improvement score.
- Presence of exclusion criteria.
- Concomitant current use of other medications.
- Quality of life assessment (SF-36).
- Adverse events/drug reactions/special situations.
- Change in therapy with agomelatine if occurred or required.

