#### **Biometrics**

- Due to the non-interventional nature of this study, statistical analysis will be conducted in a descriptive and searchable form. All indicators will be analyzed using descriptive statistics methods. For each indicator, the number of patients, the average value, the standard error, the minimum and maximum values, or the proportion of each category will be specified. All composite indicators will be
- listed and presented in visual form as graphs and frequency distribution tables / indicator tables.
- Absolute and percentage frequencies will be calculated for categorical variables. Only patients for whom data on the corresponding variables will be available will be included in the relative frequency calculations.
- All reports of adverse drug reactions, adverse events, and special situations will be coded using MedDRA, and the results will be listed and classified according to classes for organ and organ systems (system-Organ-Class; SOC) by the statisticial agency during preparation of final report.

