# Assessment of the severity of condition using Hamilton Depression Rating Scale:

- 0-7 «normal» (no marked symptoms of anxiety and depression)
- 8-15 «mild depression»
- 16-24 «moderate depression»
- 25 and more «severe depression»

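### Exclusion criterion 1, checked only after baseline, can be read to remove patients whose depression becomes severe, and the plan does not say what happens to their data

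*Combined protocol and SAP*

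**What the plan says.** The protocol keeps two lists. Non-inclusion criteria are checked at the inclusion visit. For the other list, the Table 1 row "Assessment in accordance to exclusion criteria" is marked at weeks 2, 4 and 8 and not at inclusion. The data lists for all three follow-up visits repeat the item ("Presence of exclusion criteria"), next to HAMD-17, CGI-I and SF-36.

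- **Exclusion criterion 1:** "Patients with severe/decompensated psychiatric, somatic or neurological disorders".
- **Parallel non-inclusion criterion 6:** "Severe or decompensated somatic or neurological disorders". Psychiatric disorders are not named here, so that element acts only after baseline.
- **Inclusion criterion 4:** "Confirmed depression with total HAMD-17 score of 8-24 required treatment with antidepressive medicines".
- **HAMD-17 severity key, Appendix 1:** "25 and more «severe depression".
- **Primary variable:** "Mean change from baseline (BL) in total HAMD-17 score assessed at week 8 of the observational period".
- **Biometrics section:** "Only patients for whom data on the corresponding variables will be available will be included in the relative frequency calculations". No analysis set is defined, and no missing-data rule is given for the mean change.
- **Study plan and procedures:** the physician may change antidepressive treatment at any time, and this is not an exclusion criterion.

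The documents do not define severe in criterion 1 or say whether worsening of the studied episode counts. They also do not say whether meeting the criterion ends follow-up, or whether data already collected are kept.

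**The concern.** Every enrolled patient has depression, and the non-inclusion criteria already screen out suicide risk, psychotic symptoms, schizophrenia, bipolar disorder and substance abuse. Worsening of the depression itself is therefore an obvious way to become psychiatrically severe during follow-up. If sites apply criterion 1 to it, a patient can be excluded because the primary scale moved the wrong way.

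That is selection on the outcome. It differs from ordinary loss to follow-up because a criterion in the protocol triggers it. There is no control group in which the same selection would operate. Planning already allows up to 30% dropout, so these exclusions could pass as routine attrition. With about 20 centres and no definition, sites may also apply the criterion differently. Ratings that are never taken cannot be recovered at the analysis stage.

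**Working it through.** **1. The plan's own figure.** The inputs in the Statistical analysis section are a difference of 3.0, SD 3.8, one-sided alpha 0.005 and 90% power. For a one-sample t-test with n = 28, the noncentrality is (3.0/3.8) × √28 = 4.18, and the noncentral t gives power 0.90991, as stated. Inflation for dropout is 28/(1 − 0.30) = 40, also as stated. These figures are not in dispute; the point concerns who contributes to the mean.

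**2. Route from the criterion to the result.**
- Entry is allowed up to 24 and the severe band starts at 25, so a patient entering at 24 crosses with a 1-point worsening.
- If exclusion at week 2 or 4 ends follow-up, there is no week-8 HAMD-17 and no change score.
- Under the available-data rule the patient also leaves the responder and remission denominators.
- A patient first found severe at week 8 has the primary score from that visit, and is lost only if collected data are deleted.

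**3. Formula.** Let f be the share removed, R the mean change in those retained and X the mean change in those removed. The all-patient mean is (1 − f)R + fX, so improvement is overstated by f(X − R).

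**4. Size under assumed trajectories.** The documents give neither f nor X, so both were simulated (400,000 patients per row).
- Baseline follows the reference study quoted in the protocol (mean 15.3, SD 3.8), limited to 8–24. This puts 13.0% of patients at 20 or more and 4.5% at 22 or more.
- The SD of change is 3.8 (the plan's value) or 6 (assumed).
- Assumed mean changes at week 4 are −7, −4, −2 and 0 for the four week-8 scenarios in the table, with half of each at week 2.
- Assumed correlations are 0.6 between adjacent visits and 0.4 between weeks 2 and 8.
- Scores are held within 0–52, which is why the all-patient mean can fall short of its nominal value.
- Removal means HAMD-17 of 25 or more at a check.

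The first nominal change, −10.6, is the reference study's 4.7 − 15.3.

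| Nominal week-8 change | SD | Removed, wk 2/4 | Removed, any check | All-patient mean | Retained mean, wk 2/4 removal | Retained mean, any-check removal | Overstatement, wk 2/4 | Overstatement, any check | Non-responders removed, any check |
|---|---|---|---|---|---|---|---|---|---|
| −10.6 | 3.8 | 0.75% | 0.76% | −10.12 | −10.15 | −10.15 | 0.03 | 0.03 | 2.8% |
| −10.6 | 6 | 4.03% | 4.12% | −9.60 | −9.77 | −9.79 | 0.17 | 0.19 | 10.1% |
| −6 | 3.8 | 1.86% | 1.92% | −5.95 | −6.01 | −6.02 | 0.06 | 0.07 | 3.0% |
| −6 | 6 | 7.08% | 7.73% | −5.72 | −6.06 | −6.15 | 0.34 | 0.43 | 12.1% |
| −3 | 3.8 | 3.42% | 3.85% | −2.99 | −3.10 | −3.14 | 0.11 | 0.15 | 4.5% |
| −3 | 6 | 10.26% | 12.06% | −2.91 | −3.42 | −3.66 | 0.51 | 0.75 | 15.5% |
| 0 | 3.8 | 6.23% | 8.04% | 0.00 | −0.19 | −0.32 | 0.19 | 0.32 | 8.3% |
| 0 | 6 | 14.64% | 18.84% | 0.04 | −0.68 | −1.20 | 0.72 | 1.24 | 21.2% |

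Each overstatement is the all-patient mean minus the retained mean. The any-check columns assume that a week-8 score is also discarded; the week-2/4 columns assume it is kept.

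**5. Response rate.** With any-check removal and SD 6, the rate moves from 69.3% to 71.2% in the −10.6 scenario and from 11.6% to 14.2% in the no-change scenario.

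**6. Reading.** The direction favours the drug in every row. The size grows as the drug's effect shrinks, and most non-responders stay in throughout.

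**The case against.** The strongest reply is that this is an ambiguity and not a stated filter. Criterion 1 cites no scale or cut-off and does not mention the studied episode, so it can be read as concurrent illness. The severity key is a general one in the scale appendix, and nothing links it to the exclusion list. The visit lists treat the check as one more item to record beside the ratings, and no passage says that excluded patients leave the analysis. All of this stands, and it rules out three stronger readings that a reader might infer.

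- **That the plan filters out treatment failures by rule.** The documents do not say so. A non-responder who stays at 8–24 is untouched, treatment may be changed without exclusion, and lack of efficacy is itself a reportable special situation.
- **That a final score of 25 or more is lost.** HAMD-17 is recorded at the same week-8 visit as the check, and no passage says that it is deleted.
- **That the bias is large against the 3.0-point planning difference.** Assume, for example, retained patients at −8, excluded patients at +6 and 5% to 15% excluded. Then 14f gives 0.7 to 2.1 points. None of those inputs is in the documents, and +6 from the quoted mean baseline gives 15.3 + 6 = 21.3, which is below 25.

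The reply does not remove the problem. The appendix key is the only definition of severe depression in the documents, exclusion ordinarily means removal, and nothing tells sites or the statistician otherwise. Enrolling at least 100 patients against a calculated 40 improves precision but does not correct selection.

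**Conclusion.** The concern holds in limited form. A criterion checked only after baseline can be read to remove patients whose depression becomes severe or decompensated, and the plan leaves both the term and the handling of their data open. Read that way, the week-8 results would omit some of the worst outcomes and lean towards benefit.

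The documents do not allow the size to be derived. Under the assumed trajectories, the mean change is overstated by 0.03 to 0.19 points if improvement resembles the reference study. It is overstated by up to about 1.2 points if there is no mean improvement, or up to about 0.7 if week-8 scores are kept. These figures rest on the assumed baseline, SDs and correlations, on 25 as the working cut-off, and on removal ending the ratings. The bias is small where the drug works well and largest where it works least. It should be settled in the protocol, because missed ratings cannot be restored later.

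**What to change.** In the exclusion criteria and Table 1, state that meeting criterion 1 at V1–V3 through worsening of the studied depression is recorded as an outcome, with date and reason. State also that it neither ends observation nor removes the patient from the analysis. Then:

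- keep the HAMD-17, CGI-I and SF-36 taken at that visit;
- continue the scheduled ratings to week 8 where the patient agrees, whatever treatment the physician chooses;
- include all enrolled treated patients in the primary and secondary results;
- count a patient without a week-8 score after such an exclusion as a non-responder and non-remitter, and add a sensitivity analysis for the mean change;
- report exclusions by reason and visit.

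The cost is a short wording change, one reason-code field and a few more recorded routine visits. The estimate may come out slightly less favourable. No treatment decision changes.

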# Study plan and procedures

A patient with depression occurred within 3 month period after onset of confirmed COVID 19 infection who has already been recommended to initiate antidepressive treatment with agomelatine will be asked to provide a consent to participate in the study and in case of consent is positive the patient will be invited for 3 more visits starting from the date of the inclusion in the study according to clinical practice. Therefore clinical parameters needed for describing effectiveness and tolerability of agomelatine treatment will be prospectively collected at each of these visits.

Antidepressive treatment of enrolled outpatients can be modified by investigating psychiatrist or neurologist at any time of the observation if required.

Following visits are planned:

- 1. Inclusion Visit 0 (V0) inclusion in the study
- 2. Follow up Visits 1-2 (V1-V2) visits at week 2 and week 4 after V0.
- 3. Final Visit 3 (V3) visit at week 8 after V0.

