# Objectives

# **Primary objective**

• To describe the antidepressive effectiveness of agomelatine in patients with depression episode occurred after COVID-19 assessed by HAMD-17 after 8 weeks of treatment in the daily clinical practice.

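### Treatment may change at any time after entry, but the week-8 results are described as effectiveness of agomelatine, with no planned breakdown by treatment change

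*Combined protocol and SAP*

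**What the plan says.** The primary objective attributes the result to one drug: "To describe the antidepressive effectiveness of agomelatine in patients with depression episode occurred after COVID-19 assessed by HAMD-17 after 8 weeks of treatment". The secondary objectives on anxiety, global improvement and quality of life are worded the same way.

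The primary variable is "Mean change from baseline (BL) in total HAMD-17 score assessed at week 8 of the observational period". Under Secondary variables, response is a fall of at least 50% in the HAMD-17 total and remission is a total below 7, both at week 8. None of these definitions depends on what the patient is taking at week 8.

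On treatment during follow-up, Study plan and procedures states: "Antidepressive treatment of enrolled outpatients can be modified by investigating psychiatrist or neurologist at any time of the observation if required". Item 8 of the Non-inclusion criteria bars "Treatment by others psychotropic products (antipsychotics, anxiolitics etc". In Table 1 the row "Assessment in accordance to inclusion/ non- inclusion criteria" is marked at Visit 0 only. The three Exclusion criteria checked at Visits 1 to 3 cover severe or decompensated disorders, liver signs, and participation in another trial or survey. None mentions an added psychotropic or a change of antidepressant.

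The lists for Visits 1, 2 and 3 each include "Concomitant current use of other medications" and "Change in therapy with agomelatine if occurred or required". Neither Statistical analysis nor Biometrics links these records to the outcomes.

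**The concern.** A patient who does poorly on agomelatine, is given another drug and improves would still count towards the mean change, the response rate and the remission rate. The objectives would report that improvement as an effect of agomelatine. Without a comparator, the week-8 figure is the study's whole answer, so what it is taken to mean matters.

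The anxiety results are the most exposed. Anxiolytics are among the products barred at entry but not afterwards, and HAMD-17 items 10 and 11 are separate secondary variables credited to agomelatine. An anxiolytic added after Visit 0 could act directly on both.

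The plan expects some patients to leave agomelatine. Discontinuation because of adverse events is a secondary variable, one exclusion criterion refers to stopping the drug, and lack of efficacy is a reportable special situation. No rule says how a HAMD-17 score obtained after such a change is to be used or labelled.

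**Working it through.** **1. The plan's own figure.** Inputs from Statistical analysis: difference 3.0 points, SD 3.8, one-sided alpha 0.005, one-sample t-test, dropout 30%. The noncentral t distribution with N = 28 gives power 0.90991, as stated. Inflation gives 28 / (1 - 0.30) = 40, as stated. The concern does not depend on these figures, but step 5 uses the same method.

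**2. The provisions side by side.**

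| Element | Before entry | Visits 1 to 3 |
|---|---|---|
| Other psychotropics | Barred (item 8) | Not addressed |
| Modification of antidepressive treatment | Not applicable | Allowed at any time |
| Record of concomitant drugs | Yes | Yes |
| Record of change in agomelatine therapy | Not applicable | Yes |
| Use of these records in outcome analysis | None stated | None stated |

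No sentence says that scores after a change are included. That follows from variables without a treatment condition and from the absence of any analysis set or exclusion rule.

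**3. Effect on the mean, compared with the same patients staying on agomelatine alone.** Let s be the share of patients changed and e the extra HAMD-17 improvement due to the other drug. Then overstatement = s x e. The documents give neither input; the assumed ranges are s = 5% to 30% and e = 2 to 6 points.

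| s | e (points) | s x e (points) |
|---|---|---|
| 5% | 2 | 0.1 |
| 10% | 4 | 0.4 |
| 20% | 4 | 0.8 |
| 30% | 6 | 1.8 |

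For scale, the cited earlier study of agomelatine reports a fall of 15.3 - 4.7 = 10.6 points at six weeks, in depression due to neurological disease. Against that, 0.4 points is 0.4 / 10.6 = 4% and 1.8 points is 17%.

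**4. Direction against a different comparison.** Compared with patients who remain on agomelatine alone, including the changed patients shifts the mean by s x (mean improvement in changed patients - mean improvement in unchanged patients). If changed patients improve by 4 points less because they were failing and had little time on the new drug (assumed), 10% x (-4) = -0.4 points. The reported mean would then be lower than the agomelatine-alone mean. The sign therefore depends on the comparison and on data not yet seen.

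**5. Is a breakdown feasible?** With 100 patients enrolled and 30% dropout, 70 remain. If 10% to 40% of these are changed (assumed), 63 to 42 are unchanged. Power for 3.0 points with SD 3.8 at one-sided 0.005 is 0.9998 with 63 and 0.990 with 42. The changed patients would number only 7 to 28, split over two categories, so those rows can only be descriptive.

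**The case against.** Treatment changes are normal in a non-interventional study, and the objective already refers to daily practice. On that reading the week-8 mean is the outcome of a strategy that starts with agomelatine, and nothing is wrong with the estimate. This stands as a defence of keeping every patient in the analysis. It does not cover the wording of the objectives, which name the drug and not the strategy.

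The permission to modify treatment may also include changes within agomelatine therapy, which would not be misattributed. Biometrics says all indicators will be summarised descriptively, which can be read to cover recorded therapy changes and concomitant drugs. Reports of lack of efficacy will be coded and listed. The exclusion criterion "Patients with severe/decompensated psychiatric, somatic or neurological disorders" is checked at follow-up and may remove some worsening patients. Statistical analysis announces groups of patients and then runs straight into the endpoint, and whether text was lost there cannot be told. All of this stands, but none of it supplies a table of outcome by treatment status.

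A reader might infer two stronger things that the documents do not support:

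- **That the results are biased in favour of agomelatine.** This needs changes to occur, to involve another drug and to produce the gain. The documents give no rate for any of these, and step 4 shows that the sign can reverse.
- **That the response rate is overstated by 4 to 16 points.** This comes from multiplying the cited 82.33% by an assumed 5% to 20% of patients changed (4.1 to 16.5 points). It assumes that patients changed for inadequate benefit respond as often as everyone else, then recodes them all as failures. That is a different endpoint and does not estimate bias. The 82.33% is also a six-week rate from another population.

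**Conclusion.** The concern holds as a gap in what the results are said to mean and in planned reporting. As written, the plan would present improvement after a switch or an added psychotropic as effectiveness of agomelatine, with no table from which a reader could judge how much this matters.

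The size cannot be determined from the documents. Over the assumed ranges the mean change would be overstated by 0.1 to 1.8 HAMD-17 points relative to the same patients on agomelatine alone, and by 0.4 points in the 10% by 4-point example. Both inputs are assumptions, and the formula treats the other drug as beneficial. No figure for response or remission can be supported. The planned sample size is unaffected.

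**What to change.** 1. Keep all patients in the primary mean change and in the response and remission percentages as now defined. State the conclusion as the outcome of starting agomelatine in routine practice, whatever treatment follows.
2. From the concomitant-medication and therapy-change records at Visits 1 to 3, report the number of treatment changes and their timing, at least by visit interval.
3. Show week-8 HAMD-17 change (total, item 10 and item 11), response and remission by week-8 treatment status: agomelatine alone; agomelatine plus another psychotropic; agomelatine stopped or switched.
4. Count stopped, switched or augmented patients as non-responders and non-remitters only in a labelled sensitivity analysis. As the main rule it would override the plan's definitions: a patient with a 50% fall who had been given an anxiolytic would become a failure.

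No restriction on treatment is proposed, and no new visits, patients or data items are needed. The cost is analysis wording, one or two more descriptive tables and a more cautious conclusion. The subgroups will be small and are formed after baseline, so differences between them should not be read as effects of the treatments.
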